14.1 Definition of analysis sets

The Enrolled Set (ES) will consist of all subjects who have given informed consent.

The Open-Label Set (OLS) will consist of all subjects who receive at least 1 dose of study medication in the Open-Label Period of the study (Part A).

The Randomized Set (RS) will consist of all subjects randomized into Part B of the study.

The Flared Set (FS) will consist of all subjects from the RS who experience a flare in Part B.

The Part B Full-Dose Set (FDS) will include all subjects from the RS who ever received a dose of CZP Q2W during Part B (including escape treatment).

The Safety Set (SS) will consist of all subjects in the ES who have received at least 1 dose of study medication.

The Safety Set Part B (SSB) will consist of all subjects in the RS who have received at least 1 dose of study medication in the Double-Blind Period of the study (Part B).

The Full Analysis Set (FAS) will consist of all subjects in the RS who have received at least 1 dose of study medication in Part B, and have valid ASDAS measurements at Week 48 and at least 1 timepoint following Week 48.

The Per Protocol Set (PPS) will be used to evaluate the sensitivity of the results of the primary efficacy analysis, which is based only on subjects who enter Part B. As such, the PPS will consist of subjects in the FAS without any major protocol deviations that may influence the validity of the data for the primary efficacy variable. Important protocol deviations will be defined and evaluated prior to unblinding.

The Pharmacokinetic Set A (PKSA) will consist of all subjects from the OLS who provide at least 1 PK sample during Part A.

The Pharmacokinetic Set B (PKSB) will consist of all subjects from the SSB who provide at least 1 PK sample during Part B.

14.2 General statistical considerations

All efficacy analyses for Part B will be performed using the RS. The FAS and PPS will be used for a sensitivity analysis on the primary endpoint only. Efficacy summaries for variables collected in Part A will be based on the OLS.

Summaries at the Week 48 timepoint for laboratory data and data collected via electronic device (Site Tablet) will be based on the assessments conducted 3 to 5 days prior to the Week 48 clinic visit.

The statistical analysis of the primary efficacy variable will account for the testing of multiple doses by using a fixed sequence testing procedure. The proportion of subjects who do not experience a flare (where flare is defined as ASDAS ≥ 2.1 on 2 consecutive visits or ASDAS > 3.5 at any visit) will be compared between each CZP dose and placebo. The predefined order of

hypotheses testing, each at a 2-sided 0.05 significance level for the comparison between the given CZP dose and placebo, will be performed in the sequence shown below:

1. CZP 200mg Q2W vs placebo
2. CZP 200mg Q4W vs placebo

The second test will be performed irrespective of whether the first test is significant at the 0.05 level or not. However, the second test will be interpreted as statistically significant only if the first test is significant at the 0.05 level as well.

14.3 Planned efficacy analyses

14.3.1 Analysis of the primary efficacy variable

The primary efficacy variable is the proportion of subjects who do not experience a flare. The primary analysis will be based on logistic regression. The odds ratio based on the proportion of subjects who do not experience a flare will be estimated and tested between treatment groups using a logistic regression model with factors of treatment group, geographic region, and mNY criteria (yes/no). Geographic region and mNY classification are also randomization stratification factors. The use of region as a stratification variable and as a factor in the model is intended to combine study centers in similar geographic regions. The geographic regions to be used will be pre-defined in the IXRS and in the SAP. Each CZP dose will be compared against placebo to establish superiority over placebo and will be tested sequentially at an alpha of 0.05 as outlined in [Section 14.2](#).

An approach based on the principles of nonresponse imputation (NRI) will be used to impute missing values. Specifically, if a subject withdraws from Part B at any point, they will be considered as having not responded to treatment. Therefore, they will be assumed to have experienced a flare during Part B for analysis purposes. If a subject has an intermittent missing ASDAS score (ie, a missing value at 1 visit but nonmissing values at the previous and subsequent visit), then the missing value will be ignored and flare will be based on the 2 available values. If the ASDAS score is missing at 2 or more consecutive visits, then the subject will be treated as having experienced a flare (even if ASDAS scores are available after the missed visits).

Subgroup analyses based on age, gender, race, region, CRP level, ADA_b status, and mNY criteria will be performed. These analyses will be done for the primary efficacy variable and will be based on descriptive statistics only.

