3 STUDY OBJECTIVES

The following key definitions are provided as a reference for understanding the study objectives and are used throughout the protocol.

Sustained remission is achieved when a subject has an ASDAS <1.3 at Week 32 or Week 36 (if ASDAS <1.3 at Week 32, it must be <2.1 at Week 36 [or vice versa]) and at Week 48. A subject is eligible for Part B of the study only if sustained remission is achieved in Part A.

A flare occurs when a subject has an ASDAS ≥ 2.1 at 2 consecutive visits or ASDAS >3.5 at any visit during Part B.

Subjects who meet the criteria of flare during Part B and who crossed-over to full-dose treatment (CZP 200mg Q2W) are regarded as escapers.

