14.3.2.2 Part B analysis

The time to flare will be analyzed using Kaplan-Meier methods. For those who meet the criteria for flare, the time will be defined as the length in days from randomization in Part B until the visit at which the criteria for flare were met. Subjects who discontinue the study without meeting the criteria for flare will be censored at the time of their last study visit. Subjects who complete the study without meeting the criteria for flare will be censored at their Week 96 visit. Between group differences will be analyzed with the log-rank statistic.

The changes from Baseline in ASDAS, BASDAI, BASFI, and BASMI at Week 96 for the RS will be compared between treatment groups using a mixed model for repeated measures (MMRM). The pattern of missingness for these variables is assumed to be missing at random (MAR). Subjects who enter Part B will have already demonstrated sustained remission through 48 weeks on CZP 200mg Q2W. Many of these subjects will be randomized to receive placebo and will, therefore, be more likely to experience a flare. Postflare data for subjects who experience a flare (in any treatment group) will be treated as missing for the MMRM analysis. It is further assumed that most subjects who discontinue at this late stage in the study (ie, during Part B) will do so as a result of reduced efficacy. Therefore, missing efficacy data due to either flare or study treatment discontinuation should be dependent on the observed efficacy scores, but independent of unobserved data.

The MMRM model will include Baseline score as a fixed-effect covariate, treatment group, region, mNY criteria (yes/no), and visit as fixed-effect categorical factors, and Baseline-by-visit and treatment group-by-visit as interaction terms. An unstructured correlation pattern will be used to estimate the variance-covariance of the within-subject repeated measures. Tables will present the adjusted means for placebo and the CZP doses (200mg Q2W and 200mg Q4W), the respective difference to placebo, the corresponding p-value, and 95% CI.

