14.8 Determination of sample size

It is anticipated that approximately 210 subjects will be randomized in a 1:1:1 ratio to the CZP 200mg Q2W, CZP 200mg Q4W, and placebo treatment groups. The primary efficacy analysis is based on the proportion of subjects who do not experience a flare during Part B of the study. The proportion of subjects who do not experience a flare during Part B is assumed to be 80%, 75%, and 45% for the CZP 200mg Q2W, CZP 200mg Q4W, and placebo treatment groups, respectively. Given these assumptions, a sample size of 70 subjects per group provides 98% power to detect a significant difference between the CZP 200mg Q2W dose and placebo and 94% power to detect a significant difference between the CZP 200mg Q4W dose and placebo using a 2-sided significance level of 0.05.

Given that subjects enter Part B only if they have achieved sustained remission in Part A, it is necessary to estimate the number of subjects needed to enroll in Part A. It is assumed that approximately 28% of subjects enrolled in Part A will achieve sustained remission and qualify for Part B. This means that about 750 subjects will be enrolled in Part A in order to have 210 subjects who are randomized into Part B. Subject response to treatment will be evaluated on an ongoing basis as subjects enroll in Part A, and the number of subjects enrolled will be adapted accordingly in order to achieve 210 subjects randomized to Part B.

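### The primary logistic model is valid but omits Week 48 ASDAS, the pre-randomisation value of the score that defines flare; adding it would bring a modest gain in power if that value is prognostic

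*Protocol*

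**What the plan says.** Section 14.3.1 of the protocol lists the terms of the primary model: a "logistic regression model with factors of treatment group, geographic region, and mNY criteria (yes/no". It adds: "Geographic region and mNY classification are also randomization stratification factors". No measure of disease activity is in the model. Section 14.2 tests full dose and then half dose against placebo in fixed order, "each at a 2-sided 0.05 significance level for the comparison between the given CZP dose and placebo".

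The outcome comes from Section 3: "A flare occurs when a subject has an ASDAS" of 2.1 or more at two consecutive visits, or above 3.5 at any one visit. The same section admits to Part B only subjects in sustained remission, which I read as requiring ASDAS below 1.3 at Week 48. Table 5.1 (footnote a) makes the assessments 3 to 5 days before Week 48 the qualifying ones, and Section 7.10 has the IXRS calculate ASDAS throughout.

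For the continuous secondary variables, Section 14.3.2.2 states: "The MMRM model will include Baseline score as a fixed-effect covariate". That section distinguishes Baseline (Week 0) from the randomisation Baseline (Week 48). Its logistic models for the binary secondary variables use treatment, region and mNY only, as the primary model does.

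**The concern.** Because flare is an absolute threshold, ASDAS just before randomisation measures how far each subject starts from failure. With values below 1.3, the distance to 2.1 is at least 0.8 and can reach about 2, so the entry rule narrows the spread without removing it. The value is collected before randomisation and needs no new procedure.

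If it predicts flare, leaving it out forgoes some power and leaves any chance difference between arms of 70 uncorrected in the primary estimate. The matter is one of efficiency. It would count most if the true effects were weaker than planned.

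**Working it through.** **Inputs.** From Section 14.8: 70 per arm, two-sided 0.05, and "The proportion of subjects who do not experience a flare during Part B is assumed to be 80%, 75%, and 45" per cent flare-free for full dose, half dose and placebo. From Section 14.3.1: the model terms. The odds ratio for flare per SD of Week 48 ASDAS is not in the protocol. It is an assumption, varied from 1 to 3.

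**1. The plan's own figures.** For full dose, Section 14.8 claims that "a sample size of 70 subjects per group provides 98% power to detect a significant difference between the CZP 200mg Q2W dose and placebo"; for half dose its figure is 94%. The Wald test of the log odds ratio has

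SE = √[1/(70·p₁(1−p₁)) + 1/(70·0.45·0.55)], power = Φ(log OR/SE − 1.96).

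- Full dose: log OR = ln(0.80/0.20) − ln(0.45/0.55) = 1.587; SE = √(0.0893 + 0.0577) = 0.383; power 98.5%.
- Half dose: log OR = ln(0.75/0.25) − ln(0.45/0.55) = 1.299; SE = √(0.0762 + 0.0577) = 0.366; power 94.4%.

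Fisher's exact test gives 98.9% and 94.0%. The stated figures reproduce.

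**2. Power with and without the covariate.** Three-arm trials were simulated 5,000 times per setting, with a standard normal pre-randomisation covariate and marginal rates held at 80/75/45%. Both models contained treatment, a four-level region and mNY. Region and mNY were given no effect on the outcome.

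| Assumed OR for flare per SD | Full dose, planned → adjusted (%) | Half dose, planned → adjusted (%) |
|---|---|---|
| 1.0 | 99.4 → 99.3 | 96.0 → 95.9 |
| 1.25 | 99.2 → 99.3 | 95.5 → 95.7 |
| 1.5 | 99.0 → 99.1 | 95.9 → 96.4 |
| 2.0 | 99.1 → 99.5 | 95.8 → 97.0 |
| 3.0 | 99.2 → 99.7 | 95.4 → 97.9 |

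The Monte Carlo SE at 96% is √(0.96·0.04/5000) = 0.3 point. Within a row both models were fitted to the same data, so the change is more reliable than the levels.

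**3. Weaker effects (assumed 65/60/45%).** At odds ratios of 1.5, 2 and 3:
- Full dose: 66.3 → 67.9, 65.6 → 69.7 and 67.0 → 75.5%, gains of 1.6, 4.1 and 8.5 points.
- Half dose: 43.1 → 44.6, 42.0 → 44.9 and 42.8 → 50.7%, gains of about 1.4, 2.9 and 7.9 points.

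**4. Type I error.** With all arms at 45%, rejection was 4.6 to 5.7% for the planned model and 4.9 to 5.6% for the adjusted one.

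**5. What happens to the odds ratio.** For full dose, the median log odds ratio and its SE moved as follows:
- OR 1.5: 1.638 (0.394) to 1.706 (0.406)
- OR 2: 1.648 (0.395) to 1.819 (0.423)
- OR 3: 1.642 (0.395) to 2.037 (0.458)

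The SE rises, but the estimate rises more: at OR 3 the ratio goes from 1.642/0.395 = 4.16 to 2.037/0.458 = 4.45. That is where the power comes from.

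**6. Chance imbalance.** The difference in covariate means between two arms has SD √(2/70) = 0.17 SD units, so its 95% range is ±1.96·0.17 = ±0.33. At OR 2 per SD, the edge of that range corresponds to 0.33·ln 2 = 0.23 on the log-odds scale, which the planned model does not correct.

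**7. Second check on a truncated range.** Week 48 ASDAS was taken as uniform on 0.3 to 1.3, with odds ratios of 2, 3 and 4 per 0.5 unit and 2,500 trials per setting. The SD is 1/√12 = 0.289, so these equal 2^0.577 = 1.5, 3^0.577 = 1.9 and 4^0.577 = 2.2 per SD. Half-dose power went from 95.6 to 95.9, 95.2 to 96.8 and 95.8 to 97.6%. The variance of the standardised half-dose-minus-placebo difference was 3, 8 and 12% larger without the covariate, and unchanged (ratio 0.995) with no association.

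**The case against.** The strongest reply is that nothing here is wrong. The model is pre-specified, contains both stratification factors and holds its type I error. It also matches the binary secondary analyses in Section 14.3.2.2. All of that stands, and a reader who inferred that the primary test is invalid would be mistaken.

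Four further inferences are tempting and not supported.

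- **The odds ratio loses precision without the covariate.** The opposite holds for its log-scale SE, because the odds ratio is non-collapsible (step 5). The gain is in power and in the standardised difference, which Section 14.3.1 does not currently request.
- **The change is free.** It makes the odds ratio conditional on one more variable and moves it further from the marginal proportions behind Section 14.8. It also needs a missing-value rule: under Section 14.1 the FAS requires a valid Week 48 ASDAS, while the Randomized Set, used for the primary analysis, does not. Since entry depends on the value, gaps should be rare.
- **The MMRM sets a precedent.** Its Baseline is Week 0 and its outcome is a change from that value, so it is not the same covariate.
- **The full-dose versus half-dose comparison would benefit.** That was not calculated. Section 14.8 gives no power for it, and the formal testing in Section 14.2 covers only the two placebo contrasts.

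The prognostic strength is also assumed. The entry rule truncates the range, and Section 14.3.1 counts withdrawal, or missing ASDAS at two or more consecutive visits, as flare whatever the starting score. Both could weaken the association. This limits the size of the point but does not remove it, because almost nothing is lost if the association is absent.

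**Conclusion.** The point holds as a modest improvement to a valid analysis. At the planned rates the gain is about 0 to 2.5 points of power for half dose and at most 0.5 point for full dose, from levels already above 95% in the simulations. If the true rates were 65/60/45%, it would be about 1.5 to 8.5 points. Correction of chance imbalance comes with it.

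These sizes rest on three assumptions: an odds ratio for flare between 1 and 3 per SD (1.5 to 3 for the weaker effects), a roughly linear effect on the log-odds scale, and the same association in every arm. The protocol supports none of the three with data, so the range should be read as a range. The direction does not depend on the exact value.

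**What to change.** Before unblinding:

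1. Add ASDAS from the assessment 3 to 5 days before Week 48 as a continuous covariate in the Section 14.3.1 model, beside treatment, region and mNY.
2. From the same model, report flare-free percentages and differences standardised over the Randomized Set, and name the variance method. These stay on the scale of the Section 14.8 assumptions.
3. State a simple rule, such as imputing the overall mean, for any randomised subject without a valid value, so that the Randomized Set is kept whole.

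The cost is one model term, one further output and one sentence on missing values, with no new data and no change in sample size. The odds ratio must be labelled as conditional on Week 48 ASDAS as well as region and mNY, and its log-scale SE will be larger. Adding the covariate only in a supportive analysis would show the effect of imbalance but would add no power to the primary test.

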14.3.2 Analysis of the secondary efficacy variables

14.3.2.1 Part A analysis

The secondary efficacy variables defined in Part A are as follows:

- Percentage of subjects achieving sustained remission at Week 48
- ASDAS disease activity (ASDAS-ID and ASDAS-MD, ASDAS-HD, ASDAS-vHD) at Week 48
- ASDAS clinical improvement (ASDAS-MI and ASDAS-CII) at Week 48

The percentage of subjects achieving sustained remission, ASDAS-MI, and ASDAS-CII at Week 48 will be summarized using descriptive statistics (counts and percentages). Separate summaries will be done using NRI and observed case data.

Ankylosing Spondylitis Disease Activity Score disease activity at Week 48 will also be summarized using descriptive statistics, where counts and percentages are reported for each of the 4 categories. Two summaries will be provided: One will derive disease activity at Week 48 using last observation carried forward (LOCF, impute using the last post-Baseline nonmissing result) for missing values and the other will be based on observed case data.

All summaries of secondary efficacy variables in Part A will be based on the OLS.

14.3.2.2 Part B analysis

The time to flare will be analyzed using Kaplan-Meier methods. For those who meet the criteria for flare, the time will be defined as the length in days from randomization in Part B until the visit at which the criteria for flare were met. Subjects who discontinue the study without meeting the criteria for flare will be censored at the time of their last study visit. Subjects who complete the study without meeting the criteria for flare will be censored at their Week 96 visit. Between group differences will be analyzed with the log-rank statistic.

The changes from Baseline in ASDAS, BASDAI, BASFI, and BASMI at Week 96 for the RS will be compared between treatment groups using a mixed model for repeated measures (MMRM). The pattern of missingness for these variables is assumed to be missing at random (MAR). Subjects who enter Part B will have already demonstrated sustained remission through 48 weeks on CZP 200mg Q2W. Many of these subjects will be randomized to receive placebo and will, therefore, be more likely to experience a flare. Postflare data for subjects who experience a flare (in any treatment group) will be treated as missing for the MMRM analysis. It is further assumed that most subjects who discontinue at this late stage in the study (ie, during Part B) will do so as a result of reduced efficacy. Therefore, missing efficacy data due to either flare or study treatment discontinuation should be dependent on the observed efficacy scores, but independent of unobserved data.

The MMRM model will include Baseline score as a fixed-effect covariate, treatment group, region, mNY criteria (yes/no), and visit as fixed-effect categorical factors, and Baseline-by-visit and treatment group-by-visit as interaction terms. An unstructured correlation pattern will be used to estimate the variance-covariance of the within-subject repeated measures. Tables will present the adjusted means for placebo and the CZP doses (200mg Q2W and 200mg Q4W), the respective difference to placebo, the corresponding p-value, and 95% CI.

Change from Baseline in SIJ SPARCC and spine ASpIMRI-a in the Berlin modification scores at Week 96 will be compared between treatment groups using analysis of covariance (ANCOVA) for observed values only (ie, no imputation). The model will include Baseline score, treatment group, region, and mNY criteria (yes/no). Tables will present the adjusted means for placebo and the CZP doses (200mg Q2W and 200mg Q4W), the respective difference to placebo, the corresponding p-value, and 95% CI.

The binary secondary efficacy variables (ASDAS-MI, ASDAS-CII, ASAS20, ASAS40, ASAS5/6, ASAS PR, and BASDAI50 response) at Week 96 will be analyzed using a logistic regression. The odds ratio of the responder rates at Week 96 will be estimated and tested

between treatment groups using a logistic regression model with factors of treatment group, region, and mNY criteria (yes/no). Tables will present the responder rates for placebo, CZP 200mg Q2W, and CZP 200mg Q4W, the respective effect estimates (adjusted odds ratio with reference to placebo), p-values, and 95% CIs. Subjects with a missing responder status at Week 96 will be treated as a nonresponder for analysis purposes (ie, NRI).

Ankylosing Spondylitis Disease Activity Scores (ASDAS-ID, ASDAS-MD, ASDAS-HD, ASDAS-vHD) will be summarized by treatment group using summary statistics (counts and percentages) based on observed case data.

In addition to the analyses mentioned above, descriptive statistics (number of available observations [n], mean, median, SD, minimum, and maximum) will be provided by treatment group for the secondary efficacy variables. The descriptive analyses will be covered in the tables summarizing the variables over time. This will include a summary of the actual values, change from Baseline (Week 0), and change from randomization Baseline (Week 48). The statistical comparisons described for secondary efficacy variables are not part of the multiplicity-controlled testing procedure described in [Section 14.2](#). The p-values reported for these analyses will not be adjusted for multiplicity and will be considered nominal. All analyses and summaries of secondary efficacy variables in Part B will be based on the RS.

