14.6 Handling of dropouts or missing data

For the primary efficacy variable (percentage of subjects in Part B who do not experience a flare), an approach based on the principles of NRI will be used to impute missing values. Specifically, if a subject withdraws from Part B at any point, they will be considered as having not responded to treatment. Therefore, they will be assumed to have experienced a flare during Part B for analysis purposes. If a subject has an intermittent missing ASDAS score (ie, a missing value at 1 visit but nonmissing values at the previous and subsequent visit), then the missing value will be ignored and flare will be based on the 2 available values. If the ASDAS score is missing at 2 or more consecutive visits, then the subject will be treated as having experienced a flare (even if ASDAS scores are available after the missed visits).

For the time to flare endpoint, the rules as described above for the primary endpoint will be applied to account for missing data when determining whether or not a subject experienced a flare. Subjects who discontinue the study without meeting the criteria for flare will be censored

at the time of their last study visit. Subjects who complete the study without meeting the criteria for flare will be censored at their Week 96 visit.

Selected continuous secondary efficacy variables will be analyzed using MMRM methods (see [Section 14.3.2.2](#) for details). Missing data for binary response secondary efficacy variables will be handled using NRI. Secondary variables related to MRI will be analyzed based on the observed case data.

In general, other efficacy variables will be summarized as both observed case and with imputation (NRI for binary response variables and LOCF for continuous variables), unless otherwise specified. Nonresponse imputation is implemented by treating missing data for binary response variables as a nonresponse. The LOCF summaries will impute missing continuous data using the last post-Baseline nonmissing result. In the event that a subject has no post-Baseline data for a given continuous variable, no imputation will be performed.

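### Section 14.6 both counts withdrawals as flares and censors them in the time-to-flare analysis, and imputed flares have no event date

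*Protocol*

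**What the plan says.** Time to flare is the first secondary variable listed for subjects entering Part B (protocol Section 4.1.2.2). It is to be analysed by Kaplan-Meier, and "Between group differences will be analyzed with the log-rank statistic" (Section 14.3.2.2).

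Section 14.6 sets the primary endpoint's missing-data rules first. On withdrawal: "if a subject withdraws from Part B at any point, they will be considered as having not responded to treatment". It continues: "Therefore, they will be assumed to have experienced a flare during Part B for analysis purposes". A subject whose ASDAS is missing at two or more consecutive visits is also treated as having flared, even if later scores exist.

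The next paragraph turns to the secondary endpoint: "For the time to flare endpoint, the rules as described above for the primary endpoint will be applied to account for missing data", in order to decide whether a subject flared. It then says: "Subjects who discontinue the study without meeting the criteria for flare will be censored at the time of their last study visit". Those who complete without meeting the criteria are censored at Week 96. Section 14.3.2.2 repeats both censoring sentences. It defines event time as days from randomisation to the visit at which the flare criteria were met, and gives no other event date.

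**The concern.** The same subject falls under two instructions. Someone who withdraws with no observed flare is an event under the carried-over rule and censored under the sentence that follows it. Someone who misses two consecutive ASDAS visits and then reaches Week 96 without an observed flare is an event under one rule and censored at Week 96 under the other. Even if the carried-over rule is meant to govern, it cannot be run as written, because an imputed flare has no date.

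The protocol fixes these rules itself, so this is not a gap left for the SAP to fill: an SAP cannot follow both. If the choice stays open until unblinding, it could be made with results in view.

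The censoring option has a further difficulty. In its argument for the MMRM, Section 14.3.2.2 assumes that "most subjects who discontinue at this late stage in the study (ie, during Part B) will do so as a result of reduced efficacy". Those are the same discontinuations. Kaplan-Meier and an unadjusted log-rank test need censored subjects to carry the same flare risk as those who remain.

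**Working it through.** **The text.** There are three ways to reconcile the sentences:

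- Meeting the flare criteria includes imputed flares. Every discontinuer is then already an event, and the censoring sentence applies to nobody.
- It means observed flares only. The withdrawal rule just carried over then has no effect.
- Only the missed-visit rules were meant to carry over. The text does not say so, and those imputed flares would still lack a date.

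**The plan's own figure.** Section 14.8 gives no event count or power for time to flare. It gives 98% and 94% power for the primary comparisons, with 70 per arm, flare-free rates of 80%, 75% and 45%, and two-sided 0.05. A Wald test of the log odds ratio gives, for full dose:

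- log OR = ln(0.80/0.20) − ln(0.45/0.55) = 1.587
- SE = √[1/(70×0.80×0.20) + 1/(70×0.45×0.55)] = 0.383
- power = Φ(1.587/0.383 − 1.96) = 98.5%

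The half dose gives 94.4% by the same formula. The stated figures reproduce, so the sample size is not in question.

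**The two rules on the same data.** Inputs from Section 14.8 are the flare-free rates S above and n = 70 per arm. Assumptions are:

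- the planning rates are read as flare-free with withdrawal counted as flare
- hazards are constant over the 48 weeks of Part B
- flare and withdrawal are independent competing causes
- a proportion w of each arm withdraws before flaring; the protocol states no rate, so w is varied.

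Rule 1, withdrawal is an event:

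- HR = ln S_active / ln S_placebo
- events = 70×[(1 − S_active) + (1 − S_placebo)]
- full dose: ln 0.80 / ln 0.45 = 0.223/0.799 = 0.28; events 70×(0.20 + 0.55) = 52.5
- half dose: ln 0.75 / ln 0.45 = 0.288/0.799 = 0.36; events 70×(0.25 + 0.55) = 56

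Rule 2, withdrawal is censored. Let f = (1 − S − w)/(1 − S), the share of an arm's events that are flares. Then:

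- Kaplan-Meier at Week 96 = S^f
- HR = (rule 1 HR) × f_active/f_placebo
- events = 70×Σ(1 − S − w)

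Full dose against placebo:

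| Assumed withdrawal, active / placebo | Events | Flare-free at Week 96 | HR |
|---|---|---|---|
| Rule 1 (any split) | 52.5 | 80% vs 45% | 0.28 |
| Rule 2, 5% / 5% | 45.5 | 84.6% vs 48.4% | 0.23 |
| Rule 2, 10% / 10% | 38.5 | 89.4% vs 52.0% | 0.17 |
| Rule 2, 5% / 10% | 42.0 | 84.6% vs 52.0% | 0.26 |
| Rule 2, 5% / 15% | 38.5 | 84.6% vs 55.9% | 0.29 |

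For the 10% / 10% row: f = 0.10/0.20 = 0.50 and 0.45/0.55 = 0.818; 0.80^0.50 = 0.894; 0.45^0.818 = 0.520; HR = 0.279 × 0.50/0.818 = 0.17; events 70×(0.10 + 0.45) = 38.5.

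For the half dose, rule 2 gives an HR from 0.26 (10% / 10%) to 0.40 (5% / 15%). In the latter case events fall from 56 to 42, and power by the Schoenfeld formula from 96.9% to 85.1%.

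**Direction.** Rule 2 moves the HR towards 1 only when f_active exceeds f_placebo, that is, when withdrawals are a larger share of events on placebo. At 5% / 10% the ratio is 0.750/0.818, below 1, and the HR moves from 0.279 to 0.256. At 5% / 15% it is 0.750/0.727, above 1, and the HR moves to 0.288.

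**The case against.** The strongest reply is that censoring is the specific rule, stated identically in two sections, and that a censored analysis is a legitimate complement to a primary analysis that imputes failure. Section 6.3.1 also lists withdrawal for pregnancy, tuberculosis, withdrawn consent and sponsor request, and dating those as flares would distort the curve. This stands as an argument about which rule to prefer. It does not remove the sentence that carries over the opposite rule.

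Design features also limit the censoring problem. Subjects who flare stay in the study on full dose (Sections 5.1.3 and 6.3.2). The ASDAS inputs are collected about every four weeks (Sections 8.3.1 and 8.4.2). Withdrawn subjects are to complete the Withdrawal Visit (Sections 6.3.1 and 8.7), so some will be observed flares. The assumption about reduced efficacy was written to support missing at random for the MMRM. All of this stands as a limit on size. But the MMRM conditions on the observed scores, whereas an unadjusted Kaplan-Meier or log-rank analysis does not.

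Three stronger inferences are tempting, and the documents do not support them:

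- *That censoring biases the comparison towards no difference.* The table shows the hazard ratio moving either way. At 5% / 10% the Week 96 difference shrinks from 35 to 32.6 points while the hazard ratio moves away from 1.
- *That 52% against 45% on placebo measures the bias.* Under the independent hazards used here, 52% is the correct flare-only probability, so the gap separates two event definitions. It would be bias in full only if every withdrawn subject would have flared by Week 96.
- *That the log-rank test is wrongly unstratified.* Section 14.3.1 notes that "Geographic region and mNY classification are also randomization stratification factors", but Section 14.3.2.2 does not say whether the test is stratified. An unstratified test would be valid, and the detail can sit in the SAP.

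**Conclusion.** The contradiction is real and lies in the protocol's current text: Section 14.6 contradicts itself, and its carried-over rule contradicts Section 14.3.2.2. The missing event date for imputed flares is a second defect in the same rule. The consequence is not negligible. Across the assumed withdrawal rates, the full-dose hazard ratio is 0.28 under one rule and between 0.17 and 0.29 under the other, with 52.5 events against 38.5 to 45.5. These figures rest on assumed withdrawal rates, constant hazards and independent causes, and they show how far the two definitions diverge.

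If censoring is the rule used, the protocol's own assumption about discontinuations makes it likely that the flare-free curves are too high. By how much cannot be derived from the documents.

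Severity is moderate. Section 14.3.2.2 places secondary comparisons outside the multiplicity-controlled procedure and calls their p-values nominal. The primary test, its alpha and its power are unaffected.

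**What to change.** Before unblinding, amend Sections 14.3.2.2 and 14.6 together:

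- State one main rule for subjects who withdraw from Part B without an observed flare, and one for subjects with two or more consecutive missed ASDAS visits, including those who go on to complete Week 96. Counting withdrawal as an event at the last Part B visit would match the primary analysis. Censoring is also open to the sponsor, provided that the carry-over sentence is then cut back to fit.
- Give an event date for every kind of imputed flare that the main rule keeps, for example the first missed visit where consecutive visits are missing.
- Report the other rule as a sensitivity analysis.

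The cost is a wording change and one extra run. If withdrawal becomes an event, the reported flare-free curves may be slightly less favourable.
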